# 3. GENETIC RESEARCH PLAN AND PROCEDURES

# **3.1** Selection of genetic research population

This appendix to the Clinical Study Protocol has been subjected to peer review according to AstraZeneca and Bristol-Myers Squibb standard procedures.

The patient will be asked to participate in this genetic research at Visit 1. If the patient agrees to participate, a single blood sample will be taken for genetic research at Visit 1. If the sample is not drawn at visit 1, it may be drawn at any other scheduled visit after Visit 1 until Visit 11.

# 3.1.1 Study selection record

All patients will be asked to participate in this genetic research. Participation is voluntary and if a patient declines to participate there will be no penalty or loss of benefit. The patient will not be excluded from any aspect of the main study.

# 3.1.2 Inclusion criteria

For inclusion in this genetic research, patients must fulfil all of the inclusion criteria described in the main body of the Clinical Study Protocol and provide informed consent for the genetic sampling and analyses.

# 3.1.3 Exclusion criteria

Exclusion from this genetic research may be for any of the exclusion criteria specified in the main study or any of the following:

- Previous bone marrow transplant
- Non-leukocyte depleted whole blood transfusion in 120 days of genetic sample collection

# **3.1.4 Discontinuation of patients from this genetic research**

A specific reason for discontinuing a patient from this genetic research is withdrawal of consent for genetic research.

Patients may withdraw from this genetic research at any time, independent of any decision concerning participation in other aspects of the main study. Voluntary discontinuation will not prejudice further treatment. Procedures for discontinuation are outlined in Section 7.8 of the main Clinical Study Protocol.

# **3.2** Collection of samples for genetic research

The blood sample for genetic research will be obtained from the patients at Visit 1. If the patient agrees to participate, a single blood sample will be taken for genetic research at Visit 1. If the sample is not drawn at Visit 1, it may be drawn at any other scheduled visit until the last study visit.

Although genotype is a stable parameter, early sample collection is preferred to avoid introducing bias through excluding patients who may withdraw due to an adverse event, such patients would be important to include in any genetic analysis. If for any reason the sample is not drawn at Visit 1, it may be taken at any visit until the last study visit. Only one sample should be collected per patient for genetics during the study. Samples will be collected, labelled, stored and shipped as detailed in the Laboratory Manual.

# **3.3** Coding and storage of DNA samples

The processes adopted for the coding and storage of samples for genetic analysis are important to maintain patient confidentiality. Samples will be stored for a maximum of 15 years following the finalisation of the Clinical Study Report, after which they will be destroyed. DNA is a finite resource that is used up during analyses. Samples will be stored and used until no further analyses are possible or the maximum storage time has been reached.

For all samples, irrespective of the type of coding used, the DNA will be extracted from the blood sample. The DNA sample will be assigned a unique number replacing the information on the sample tube. Thereafter, the DNA sample will be identifiable by the unique DNA number only. The DNA number will be used to identify the sample and corresponding data at the Bristol-Myers Squibb and/or at AstraZeneca genetics laboratories, or at the designated contract laboratory. No personal details identifying the individual will be available to any person (AstraZeneca employee or contract laboratory staff working with the DNA).

The samples and data for genetic analysis in this study will be de-identified.

The link between the patient enrolment/randomisation code and the DNA number will be maintained and stored in a secure environment OUTSIDE of the Clinical Genotyping Group Laboratory Information Management System database at AstraZeneca. The link file will be used to identify the relevant DNA samples for analysis, facilitate correlation of genotypic results with clinical data, allow regulatory audit and trace samples for destruction in the case of withdrawal of consent.

This will require each blood sample to be double coded and labelled with a second unique identifier. The sample and data will not be labelled with a personal identifier. The study number and patient number will be linked to this second unique identifier. The Investigator will not be able to link the blood sample to the patient. The link between the clinical study/patient number and the unique second number will be maintained by the Bristol-Myers Squibb Sample Bank, but unknown to the Investigator.

Once DNA is extracted from the de-identified blood sample it is given another unique identifier. The DNA number will be used to identify the sample and corresponding data at the designated contract laboratory. No personal details identifying the individual donor will be available to any AstraZeneca or Bristol-Myers Squibb employee or external provider working with the DNA. A link between the blood sample and the DNA extracted from the sample will be maintained in a confidential link file.

All genetic samples will be stored under secure conditions with restricted access at Bristol-Myers Squibb and/or AstraZeneca. The blood or data derived from the samples may be made available to groups or organisations working with Bristol-Myers Squibb and AstraZeneca on this study or as part of the development drug project. However, the samples and any results will remain the property of Bristol-Myers Squibb and AstraZeneca at all times. Bristol-Myers Squibb or AstraZeneca will not give blood, DNA samples or data derived from the samples to any other parties, except as required by law. All samples and DNA will be destroyed within 15 years following the finalisation of the Clinical Study Report or according to local legislation. Samples may be destroyed prior to this timeframe if the patient has withdrawn consent.

# 4. ETHICAL AND REGULATORY REQUIREMENTS

The principles for ethical and regulatory requirements for the study, including this genetics research component, are outlined in Section 8 of the main Clinical Study Protocol.

# 4.1 Informed consent

The genetic component of this study is optional and the patient may participate in other components of the main study without participating in the genetic component. To participate in the genetic component of the study the patient must sign and date both the consent form for the main study and the genetic component of the study. Copies of both signed and dated consent forms must be given to the patient and the original filed at the study centre. The principal investigator(s) is responsible for ensuring that consent is given freely and that the patient understands that he/she may freely discontinue from the genetic aspect of the study at any time.

# 4.2 Patient data protection

Bristol-Myers Squibb or AstraZeneca will not provide individual genotype results to patients, any insurance company, any employer, their family members, general physician or any other third party, unless required to do so by law.

Extra precautions will be taken to preserve confidentiality and prevent genetic data from being linked to the identity of the patient. In exceptional circumstances, however, certain individuals might see both the genetic data and the personal identifiers of a patient. For example, in the case of a medical emergency, an Bristol-Myers Squibb and/or an AstraZeneca Physician or an Investigator might know a patient's identity and also have access to his or her

genetic data. Also regulatory authorities may require access to the relevant files, though the patient's medical information and the genetic files would remain physically separate.

# 5. DATA MANAGEMENT

Any genotype data generated in this study will be stored in the Bristol-Myers Squibb or other appropriate secure system within Bristol-Myers Squibb and/or AstraZeneca and/or third party contracted to work with Bristol-Myers Squibb and/or AstraZeneca to analyse the samples.

The results from this genetic research may be reported in the Clinical Study Report for the main study, or in a separate report as appropriate.

Some or all of the clinical datasets from the main study may be merged with the genetic data in a suitable secure environment separate from the clinical database.

# 6. STATISTICAL METHODS AND DETERMINATION OF SAMPLE SIZE

The number of patients who will agree to participate in the genetic research is unknown. It is therefore not possible to establish whether sufficient data will be collected to allow a formal statistical evaluation or whether only descriptive statistics will be generated. A statistical analysis plan will be prepared where appropriate.

# 1. DEFINITIONS OF CARDIOVASCULAR EVENTS

The D1680C00003 study (SAVOR-TIMI 53) definitions for cardiovascular endpoints are based on definitions developed at the TIMI Study Group. These definitions have evolved with experience in order to 1) incorporate improved diagnostic techniques, 2) emphasize specificity in identifying true cardiovascular events, and 3) permit implementation in large multinational, multicenter clinical trials.

# **1.1 Myocardial Infarctions**

All myocardial infarctions (MIs) will be counted as events whether they represent the reason for the hospitalisation or occurred during a hospitalisation. In addition, they will be counted as events whether they occurred spontaneously or as the direct consequences of an investigation/procedure or operation. In order to meet the criteria as an endpoint, an MI must be distinct from the qualifying event (ie, re-infarction for a patient who qualified for the study based on recent MI). The definition of MI as an endpoint will take into account whether a patient had a recent MI or has undergone revascularisation with percutaneous coronary invention (PCI) or coronary artery bypass graft (CABG) surgery. In cases where both cardiac troponin and CK-MB are available (drawn at similar time points) and are discordant, biomarker criteria will be applied using cardiac troponin. The definitions of MI are as follows for the 4 clinical settings in which it may occur:

A. **Spontaneous MI (normal biomarkers)** - For patients with no recent revascularisation in whom biomarkers were never elevated or have been documented to return to normal after a qualifying (or recent) MI, criteria 1 and 2 or criterion 3 or criterion 4 must be met:

- 1. Typical cardiac biomarker rise and/or fall with the following degrees of elevation accepted as biochemical evidence of myocardial necrosis (either one or both):
  - Troponin T or I: maximal concentration greater than the MI decision limit
  - CK-MB: maximal concentration greater than the ULN

AND

- 2. At least 1 of the following additional supportive criteria:
  - (a) Ischaemic discomfort at rest lasting >10 minutes or
  - (b) ECG changes indicative of ischaemia (ST elevation > 0.1 mV or ST depression > 0.05 mV, or new T-wave inversions)

OR

3. Development of new, abnormal Q waves (>30 msec in duration and >1 mm in depth) in >2 contiguous precordial leads or >2 adjacent limb leads; or increase R amplitude in V1-V3 consistent with posterior infarction

OR

4. Pathologic findings of an acute MI.

B. **Spontaneous MI (Elevated biomarkers)** - For patients with no recent revascularisation in whom biomarkers from a qualifying (or recent) MI remain elevated, criteria 1 and 2, or criterion 3, or criterion 4 must be met:

1. Cardiac biomarker re-elevation defined as:

- (a) Increase by at least 20% of the previous value; and
- (b) Documentation that the biomarker assayed was decreasing prior to the suspected new MI;

### AND

- 2. At least 1 of the following additional supportive criteria:
  - (a) Ischaemic discomfort at rest lasting >10 minutes; or
  - (b) ECG changes indicative of ischaemia (ST elevation > 0.1 mV or ST depression > 0.05 mV, or new T-wave inversions);

### OR

3. Development of new, abnormal Q waves (>30 msec in duration and >1 mm in depth) in >2 contiguous precordial leads or >2 adjacent limb leads; or increase R amplitude in V1-V3 consistent with posterior infarction;

OR

4. New elevation of ST-segments > 0.1 mV in > 2 contiguous precordial or adjacent limb leads

### AND

- (a) Ischaemic discomfort at rest lasting > 20 minutes; or
- (b) Ischaemia-mediated new hemodynamic decompensation requiring pharmacologic or mechanical support; or
- (c) Angiographic evidence of acute coronary occlusion

C. Within 24 hours after PCI a patient must have EITHER:

1. CK-MB >3× ULN and, if the pre-PCI CK-MB was >ULN, both an increase by at least 50% over the previous value and documentation that CK-MB was decreasing prior to the suspected recurrent MI;

OR

2. Pathologic findings of an acute MI.

Note: symptoms are not required.

- D. Within 24 hours after CABG a patient must have EITHER:
- 1. CK-MB >5× ULN and, if the pre-CABG CK-MB was >ULN, both an increase by at least 50% over the previous value and documentation that CK-MB was decreasing prior to the suspected recurrent MI;

### AND

- 2. At least one of the following supportive criteria:
  - (a) Development of new, abnormal Q waves (>30 msec in duration and >1 mm in depth) in >2 contiguous precordial leads or >2 adjacent limb leads; or increase R amplitude in V1-V3 consistent with posterior infarction, or
  - (b) Angiographically documented new graft or native coronary occlusion, or
  - (c) Imaging evidence of new loss of viable myocardium

OR

3. Pathologic findings of an acute MI.

Note: symptoms are not required.

Note: If cardiac troponin measurements are the only cardiac biomarker data available, they may be used by the Clinical Event Adjudication Committee (CEC), along with the ECG and clinical scenario, in the adjudication of suspected MI after revascularisation (PCI or CABG).

The reviewers should also consider the clinical features (eg, renal insufficiency), possible alternative diagnoses (eg, pericarditis), pattern of marker release (eg, absence of a rise and/or fall), and known sensitivity/specificity of the various cardiac markers in the adjudication of infarction, particularly when there is discordance in the results of multiple markers.

### **Universal Definitions of MI Criteria**

Myocardial infarctions will be also be classified according to the following universal definition of MI criteria:

- Type 1: Spontaneous MI related to ischaemia due to a primary coronary event such as plaque erosion and/or rupture, fissuring, or dissection.
- Type 2: MI secondary to ischaemia due to either increased oxygen demand or decreased supply, eg, coronary artery spasm, coronary embolism, anemia, arrhythmias, hypertension, or hypotension.
- Type 3: Sudden unexpected cardiac death, including cardiac arrest, often with symptoms suggestive of myocardial ischaemia, accompanied by presumably new ST elevation, or new LBBB, or evidence of fresh thrombus in a coronary artery by angiography and/or at autopsy, but death occurring before blood samples could be obtained, or at a time before the appearance of cardiac biomarkers in the blood.
- Type 4a: MI associated with PCI.
- Type 4b: MI associated with stent thrombosis as documented by angiography or at autopsy.
- Type 5: MI associated with CABG.

# 1.2 Stroke

Stroke is defined as an acute focal neurological deficit of sudden onset,

- (a) that is not reversible within 24 hours or results in death (in < 24 hrs) and is not due to an identifiable non-vascular cause (ie, brain tumour, trauma), or
- (b) that resolves in < 24 hrs and is accompanied by clear evidence of a new stroke on cerebral imaging

Stroke will be sub-classified into one of the following 4 groups:

**Non-hemorrhagic Cerebral Infarction** - Stroke without focal collections of intracerebral blood on a brain imaging. This category will be sub-classified into suspected embolic vs other.

**Non-hemorrhagic Infarction with Hemorrhagic Conversion** - Cerebral infarction with blood felt to represent hemorrhagic conversion and not a primary hemorrhage. Hemorrhagic conversion usually occurs on the cortical surface. Hemorrhagic conversion in the deeper brain requires evidence of nonhemorrhagic infarction in the same vascular territory. Microhemorrhages evident on MRI, whether in the cortex or deep brain structures, are not considered to be consistent with a hemorrhagic conversion endpoint.

### **Primary Hemorrhagic**

Intracerebral Hemorrhage - Stroke with focal collections of intracerebral blood seen on a brain image (CT or MRI) or a postmortem examination, not likely to represent hemorrhagic conversion. Primary hemorrhages cause hematomas which are usually easily discriminated by their subcortical location and rounded or elliptical shape. Microhemorrhages incidentally discovered on brain imaging in the absence of associated symptoms will not be considered to be a primary intracranial hemorrhage endpoint.

Subarachnoid hemorrhage - High density fluid collection in subarachnoid space on brain images or blood in the subarachnoid space on autopsy.

**Uncertain** - Any stroke without brain image (CT or MRI) or autopsy documentation of type, or if tests are inconclusive

Subdural hematoma will not be classified as a stroke but will be classified as a bleeding event (intracranial hemorrhage).

Intracerebral microhemorrhages will be classified in a separate category for analysis. Microhemorrhage is defined as rounded foci of <10 mm that appear hypointense and that are distinct from other causes of signal loss on gradient-echo MRI sequences (eg, vascular flow voids, leptomeningeal hemasidarosis, or non-hemorrhagic subcortical mineralisation).

Transient ischaemic attack is defined by:

- (a) an acute focal neurological deficit ending lasting <24 hours, and not due to an identifiable non-vascular cause (ie, brain tumour, trauma), and
- (b) absence of new infarct on brain imaging (if obtained)

# **1.3** Unstable Angina requiring Hospitalisation

### Unstable angina requiring hospitalisation is defined as

(a) No elevation in cardiac biomarkers (cardiac biomarkers are negative for myocardial necrosis)

### AND

- (b) Clinical Presentation (one of the following) with cardiac symptoms lasting  $\geq 10$  minutes and considered to be myocardial ischaemia on final diagnosis
  - 1. Rest angina or
  - 2. New-onset (< 2 months) severe angina (Canadian Cardiovascular Society Grading Scale\* (or CCS classification system) classification severity  $\geq$  III)

### AND

(c) Requiring an unscheduled visit to a healthcare facility and overnight admission (does not include chest pain observation units)

### AND

- (d) At least one of the following:
  - 1. New or worsening ST or T wave changes on ECG. ECG changes should satisfy the following criteria for acute myocardial ischaemia in the absence of LVH and LBBB:
    - (a) ST elevation

New transient (known to be < 20 minutes) ST elevation at the J-point in two contiguous leads with the cut-off points:

- $\geq 0.2 \text{ mV}$  in men or  $\geq 0.15 \text{ mV}$  in women in leads V2-V3 and/or  $\geq 0.1 \text{ mV}$  in other leads
- (b) ST depression and T-wave changes New horizontal or down-sloping ST depression  $\ge 0.05$  mV in two contiguous leads; and/or T inversion  $\ge 0.1$  mV in two contiguous leads with prominent Rwave or R/S ratio > 1.
- 2. Evidence of ischaemia on stress testing with cardiac imaging
- 3. Evidence of ischaemia on stress testing without cardiac imaging but with angiographic evidence of  $\geq$  70% lesion and/or thrombus in an epicardial coronary artery *or* initiation/increased dosing of antianginal therapy.
- 4. Angiographic evidence of  $\geq$  70% lesion and/or thrombus in an epicardial coronary artery

### **1.4 Heart Failure requiring Hospitalisation:**

Heart failure requiring hospitalisation is defined as an event that meets the following criteria:

(a) Requires hospitalisation defined as an admission to an inpatient unit or a visit to an emergency department that results in at least a 12 hour stay (or a date change if the time of admission/discharge is not available).

AND

(b) Clinical manifestations of heart failure including at least one of the following:

### New or worsening

- dyspnea
- orthopnea
- paroxysmal nocturnal dyspnea
- oedema
- pulmonary basilar crackles
- jugular venous distension
- new or worsening third heart sound or gallop rhythm, or
- radiological evidence of worsening heart failure.

AND

- (c) Additional/Increased therapy
  - 1. Initiation of intravenous diuretic, inotrope, or vasodilator therapy
  - 2. Uptitration of intravenous therapy, if already on therapy
  - 3. Initiation of mechanical or surgical intervention (mechanical circulatory support, heart transplantation or ventricular pacing to improve cardiac function), or the use of ultrafiltration, hemofiltration, or dialysis that is specifically directed at treatment of heart failure.

Biomarker results (eg, brain natriuretic peptide) consistent with congestive heart failure will be supportive of this diagnosis.

# **1.5 Definition of Coronary Revascularisation Procedure**

A coronary revascularisation procedure is defined as either CABG or a PCI (eg, angioplasty, coronary stenting). CABG is defined as the successful placement of at least one conduit with either a proximal and distal anastomosis or a distal anastomosis only. PCI is defined as successful balloon inflation with or without stenting and the achievement of a residual stenosis < 50%. The balloon inflation and/or stenting could have been preceded by device activation (eg, angiojet, directional coronary atherectomy, or rotational atherectomy).

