### 12.1.3 Endpoint definitions

All primary and secondary efficacy endpoint events are defined in Appendix G.

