### Hospitalisation

Outpatient treatment in an emergency room is not in itself a serious AE, although the reasons for it may be (eg, bronchospasm, laryngeal oedema). Hospital admissions and/or surgical operations planned before or during a study are not considered AEs if the illness or disease existed before the patient was enrolled in the study, provided that it did not deteriorate in an unexpected way during the study.

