## 1. DEFINITIONS OF PRIOR HISTORY OF VASCULAR DISEASE

- Myocardial infarction (MI)
  - Includes presumed spontaneous MI (Universal Definition, type 1 [Thygesen et al 2007]) that led to hospitalisation with a final diagnosis of MI.
  - Excludes periprocedural MI (Universal Definition, type 4 or 5) and secondary MI (Universal Definition, type 2) as a result of sepsis, anaemia, or supraventricular tachycardia, for example.
- Ischaemic stroke
  - Acute focal neurological deficit lasting more than 24 hours, which was diagnosed as being due to a cerebral lesion of vascular origin, excluding known subarachnoid haemorrhage. Wherever possible, diagnosis should be based on diagnostic neuro-imaging but in instances where this was not performed, a clinical diagnosis may be accepted.
  - Does not include strokes felt to be of cardio-embolic origin such as atrial fibrillation or valvular disease, or from other causes such as dissection.
- Percutaneous coronary intervention or coronary artery bypass graft with revascularisation of >1 artery
- Objective evidence of coronary artery disease (equal or greater than 50% stenosis) in at least 2 arteries
- Peripheral arterial obstructive disease:
  - Current symptoms of intermittent claudication
  - AND
    - Ankle brachial pressure index or toe brachial pressure index <0.90 obtained at any time in the previous 12 months, or
    - o Prior peripheral revascularisation, or
    - An amputation of the legs at any level due to arterial obstructive disease.

Clinical Study Protocol Appendix F		
Drug Substance	Saxagliptin	
Study Code	D1680C00003	
Edition Number	1.0	
Date		

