- (d) Pulmonary oedema sufficient to cause tachypnea and distress not occurring in the context of an acute myocardial infarction or as the consequence of an arrhythmia occurring in the absence of worsening heart failure
- (e) Cardiogenic shock not occurring in the context of an acute myocardial infarction or as the consequence of an arrhythmia occurring in the absence of worsening heart failure.

Cardiogenic shock is defined as systolic blood pressure (SBP) < 90 mm Hg for greater than 1 hour, not responsive to fluid resuscitation and/or heart rate correction, and felt to be secondary to cardiac dysfunction and associated with at least one of the following signs of hypoperfusion:

- Cool, clammy skin *or*
- Oliguria (urine output < 30 mL/hour) *or*
- Altered sensorium *or*
- Cardiac index  $< 2.2 \text{ L/min/m}^2$

Cardiogenic shock can also be defined as  $SBP \ge 90 \text{ mm Hg}$  as a result of positive inotropic or vasopressor agents alone and/or with mechanical support in less than 1 hour.

The outcome of cardiogenic shock will be based on CEC assessment and must occur after randomisation. Episodes of cardiogenic shock occurring before and continuing after randomisation will not be part of the study endpoint.

This category will include sudden death occurring during an admission for worsening heart failure.

4. **Death due to Cerebrovascular Event** (intracranial hemorrhage or nonhemorrhagic stroke): refers to death occurring up to 30 days after a suspected stroke based on clinical signs and symptoms as well as neuroimaging and/or autopsy, and where there is no conclusive evidence of another cause of death.

Definition of Death due to Stroke: refers to death occurring up to 30 days after a stroke that is either due to the stroke or caused by a complication of the stroke.

5. **Death due to Other Cardiovascular Causes**: death must be due to a fully documented cardiovascular cause not included in the above categories (eg, dysrhythmia, pulmonary embolism, or cardiovascular intervention).

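### The coronary revascularisation component of the first secondary endpoint does not exclude procedures already planned before randomisation

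*Protocol*

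**What the plan says.** Section 12.1.3 leaves no doubt about which text governs: "All primary and secondary efficacy endpoint events are defined in Appendix G". Appendix G 1.5 then states that "A coronary revascularisation procedure is defined as either CABG or a PCI (eg, angioplasty, coronary stenting"). It adds two technical conditions: "CABG is defined as the successful placement of at least one conduit", and "PCI is defined as successful balloon inflation with or without stenting and the achievement of a residual stenosis < 50"%. It has no condition on urgency, on new ischaemia, or on when the decision to operate was taken.

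The component enters the first secondary endpoint (section 12.1.3.2) as a hospitalisation for coronary revascularisation. Time runs from randomisation (section 11.1). Under Control of Type I error (section 12.2.3), this composite is tested at the same nominal level as the primary, in fixed order, once the primary is significant.

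On entry, Appendix E accepts as established disease "Objective evidence of coronary artery disease (equal or greater than 50% stenosis) in at least 2 arteries". Section 4.2 excludes an acute cardiac or stroke event in the two months before randomisation, but no criterion mentions a pending revascularisation.

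**The concern.** A procedure decided on before randomisation reflects disease and clinical decisions that predate study drug. If it is carried out shortly after randomisation, it becomes a first event on which treatment could have had little or no influence. It also ends that patient's follow-up for the composite.

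Other endpoint definitions in Appendix G guard against this. An MI must be separate from the qualifying event (1.1). Unstable angina must involve an unscheduled visit (1.3). For cardiogenic shock, "Episodes of cardiogenic shock occurring before and continuing after randomisation will not be part of the study endpoint" (1.6). Revascularisation is the component most easily scheduled in advance, yet it has no such limit.

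What is at stake is dilution of a confirmatory secondary comparison. Handling may also vary between sites, because the only written rule on planned operations belongs to adverse event reporting: under Appendix B, "Hospital admissions and/or surgical operations planned before or during a study are not considered AEs if the illness or disease existed" before enrolment and did not worsen unexpectedly. A site could carry that rule over to endpoint reporting, or it could report every procedure.

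**Working it through.** **Reproducing the plan's own figure.** Section 12.3 gives 1,040 primary events, hazard ratio (HR) 0.83, one-sided alpha 0.0245 and 85% power. With 1:1 allocation, Schoenfeld power is Φ(½·√D·|ln HR| − z), with z = 1.9686.
- D = 1,040, HR 0.83: power 0.850, as stated.
- Margin 1.30 with a true HR of 1: power 0.988, consistent with the stated minimum of 98%.

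The protocol's sizing is therefore not in dispute. It gives no corresponding figures for the secondary composite.

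**Assumed inputs for the composite.**
- Patients with established CV disease: 16,500 − 3,500 = 13,000 (section 3.1 totals and cap).
- Share with a procedure already planned: 0.5% to 2%. This is an assumption; the documents give no figure. It yields 13,000 × 0.005 = 65 to 13,000 × 0.02 = 260 procedures.
- Genuine composite events: 1.5 to 2 times the primary, that is 1,560 to 2,080. This is also an assumption.
- True HR 0.83, borrowed from the primary.

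**Dilution.** Genuine events are split as placebo P = D/1.83 and saxagliptin S = D − P. Planned procedures A are added equally to both arms, so the observed HR is approximately (S + A/2)/(P + A/2).

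| Genuine D | Planned A | Share of all events | Observed HR | Power |
|---|---|---|---|---|
| 1,560 | 0 | 0% | 0.830 | 95.6% |
| 1,560 | 65 | 4.0% | 740.0/885.0 = 0.836 | 94.9% |
| 1,560 | 130 | 7.7% | 772.5/917.5 = 0.842 | 94.1% |
| 1,560 | 260 | 14.3% | 837.5/982.5 = 0.852 | 92.4% |
| 2,080 | 0 | 0% | 0.830 | 98.9% |
| 2,080 | 65 | 3.0% | 975.9/1,169.1 = 0.835 | 98.7% |
| 2,080 | 130 | 5.9% | 1,008.4/1,201.6 = 0.839 | 98.4% |
| 2,080 | 260 | 11.1% | 1,073.4/1,266.6 = 0.847 | 97.9% |

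In the worst row, rounding the HR to 0.852 before computing power gives 92.6%, hence about 92 to 93%. These are stand-alone powers for the secondary test; in the plan it is reached only if the primary succeeds.

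**Cross-check in another form.** Let a share f of placebo first events be planned procedures with HR 1, so that the observed HR is (1 − f)·0.83 + f. For f = 1%, 2%, 5% and 10% this gives 0.832, 0.833, 0.839 and 0.847. With a fixed total of 2,000 events, power stays at or above 95.9%. A harsher case takes a composite with no more genuine events than the primary's 1,040 and adds the planned procedures on top; power is then 84.6%, 84.2%, 83.0% and 80.7%.

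**Limit of the model.** It treats planned procedures as purely additional. Some of those patients would later have had a genuine event that is now hidden behind the earlier one. At average risk this is about 260 × 1,560/16,500 ≈ 25 events in the worst row, so the dilution shown is slightly understated.

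**The case against.** The strongest reply is that no sentence says planned procedures count. They count by omission, and two adjudication documents are not shown: the committee manual (section 12.4.1) and the investigator manual (sections 6.1 and 6.3). This deserves weight, and the committee may in practice apply a sensible rule. But section 12.1.3 places the definitions in Appendix G, and section 12.4.1 describes the committee manual as covering responsibilities and procedures. A committee that followed the definition as written would confirm a planned procedure with admission.

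Second, the number of such patients may be small. A known stenosis is not a scheduled operation, and the two-month exclusion removes many recent acute events, which are a likely source of staged procedures. That stands, and it is why the size is given as an assumed range.

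Third, the effect is modest: power stays above the primary's 85% across the table, and revascularisation is also analysed on its own (section 12.1.3.3). This also stands.

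A reader might go further in three ways that the documents do not support as findings.
- One might infer damage to the primary endpoint and the 1.30 test, because Appendix G 1.1 says of MIs that "they will be counted as events whether they occurred spontaneously or as the direct consequences of an investigation/procedure or operation". The route exists, but post-procedural MI has its own biomarker or pathology thresholds. The documents give no basis for a count, and the number is probably small.
- One might object that a failed PCI or CABG attempt does not count. That is a definitional choice; it narrows the event set and adds no procedures unrelated to the drug.
- One might call a missing sensitivity analysis a defect. That normally belongs in the SAP, which is not at hand.

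**Conclusion.** The point holds as a gap in one definition. Appendix G 1.5 governs and does not exclude procedures planned before randomisation. Entry does not screen such patients out, and the component sits in a confirmatory endpoint.

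With blinded 1:1 randomisation, these procedures should balance between the arms. The consequence is therefore dilution and some loss of power, with no inflation of type I error. Under the assumed 65 to 260 procedures and 1,560 to 2,080 genuine events, the HR moves from 0.83 to about 0.835 to 0.852, and power falls by about 3 percentage points at most. None of the three assumptions (share planned, composite event count, true HR for the composite) comes from figures the protocol gives for this endpoint. The change is worth making because it is cheap and clear; it ranks between an optional improvement and a mild recommendation.

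**What to change.** In Appendix G 1.5, add that a revascularisation is not an endpoint event if source documents show it was planned or scheduled before randomisation, including staged completion of an earlier procedure, unless it was brought forward because of a new ischaemic event. Add a yes/no item on whether the procedure was planned before randomisation to the revascularisation CRF module and to the adjudication packet, so that the committee can apply the rule blind.

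The cost is one CRF item, one sentence of adjudication wording, and the loss of a small number of secondary events. No change to the primary endpoint, the 1.30 test or the success condition is needed for this point.
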